2.2.1.2 Subgroup analyses for safety endpoints

The following subgroup analyses will be performed for all adverse events summaries as mentioned in Section 2.6.2.1:

- age (\leq 65 years, $>$ 65 years)
- weight ($</\geq$ 40 kg, $</\geq$ 50 kg, $</\geq$ 60 kg)
- treatment regimen (overall, 1-step and 3-step titration)
- reason for switching to 3-step titration (as captured in the DAR page of CRF, e.g., adverse events, lab or test abnormality, lack of efficacy etc.)
- Patients satisfying treatment retention criteria as in Section 2.9.1 (yes/no)
- overall compliance to study medication (<75% and 75-100%)
- Patient profile analysis 1a: Use of skin moisturizer at baseline (yes/no)*
 - ◆ Total
 - ◆ Compliance to study medication (<75% and 75-100%)

Note: skin moisturizer will be identified using the data captured in the prior and concomitant medication CRF page and confirmed by the clinical team.

- Patient profile analysis 1b: Use of skin management at least one time during study period (yes/no)*

- ◆ Total
- ◆ Compliance to study medication (<75% and 75-100%)

Note: skin management will be identified using the data captured in the prior and concomitant medication CRF page and confirmed by the clinical team.

Amongst AEs of special interest,

1. Gastrointestinal symptoms will be summarized by age, weight and patient profile analysis 1a and 1b subgroups as described above,
2. Application site skin reactions and irritations will be summarized by age, weight and patient profile analysis 1a and 1b subgroups as described above.

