**Table 5-1 Dosage form and drug content for 1 step titration**

| Form                            | Loading dose / Content per one patch | Size               |
|---------------------------------|--------------------------------------|--------------------|
| Exelon ® patch 9 mg  | 9 mg rivastigmine                    | 5 cm   |
| Exelon ® patch 18 mg | 18 mg rivastigmine                   | 10 cm  |

If patients cannot tolerate 1-step titration method to reach the maintenance patch dose of 18 mg/day, the investigators can use their clinical judgement to switch those patients to slower 3-step titration method in order to reach the maintenance dose of 18 mg/day or find the highest well-tolerated dose for each individual patient. Once the dose started at 4.5 mg of rivastigmine once a day, as a general rule, the dose should be increased to 4.5 mg a day at 4-week intervals to 18 mg once a day. Those patients will be allowed to stay in the study. Patients with doses below the planned dose will continue to participate in the study.

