**5.2 Treatment arms**

This is an open-label, single arm study; all of the patients will be assigned to 1-step titration treatment.

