#### **Titration Period (Week 1 to 8)**

The day or following day (in case of a patient who takes his/her previous oral ChE inhibitors at the baseline visit) of the baseline visit (Day 1), all patients will start study treatment with one rivastigmine patch of 9 mg once a day. During the titration period, as a general rule, the dose should be increased to 18 mg once a day at 4 weeks later:

Week 1 – 4: Rivastigmine patch 9 mg/day

Week 5 – 8: Rivastigmine patch 18 mg/day

Should tolerability problems occur during the titration period, the dose can be adjusted in a range not exceeding 18 mg a day as appropriate depending on the clinical symptoms until the dose reaches the maintenance dose. In the event of gastrointestinal disorders (e.g., nausea, vomiting) or other tolerability problems, the dose should be reduced or treatment should be

temporarily interrupted until these adverse effects resolve. Patch treatment can be resumed at the same dose or previous well tolerated dose if interruption of treatment is around or within 4 days. Otherwise, treatment should be resumed at the initial starting dose (e.g. 4.5 mg or 9 mg). After treatment resumption, the dose at resumption should be maintained for a minimum of 2 weeks. If the dose is shown to be well-tolerated, the dose can be increased to the pre-resumption dose at intervals of 2 weeks or more.

Rivastigmine patch dose adjustments required for tolerability problems will be according to the dose adjustment scheme defines in [Section 5.5.5](#).

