2.2 Analysis sets

Full Analysis Set (FAS)

The FAS will include all patients who received at least one dose of study treatment and had at least a baseline and any post-baseline assessment on treatment. This is the primary analysis population and will also be used for all efficacy analyses.

Per protocol Set (PP set)

The per protocol set will include all patients in the FAS who had only 1 step titration without any major deviations from the protocol procedures. The major protocol deviations will be specified prior to database lock.

Safety Set (SAF)

The safety set will consist of all patients who received at least one dose of drug and had at least one post-baseline safety assessment.

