2.4 Treatments (study treatment, rescue medication, concomitant therapies, compliance)

2.4.1 Study treatment exposure / compliance

Duration of exposure to the study treatment (rivastigmine patch) will be calculated as the number of days exposed to the treatment with rivastigmine patch over the specified period (expressed as: Duration of exposure = last known date of rivastigmine patch administration – first known date of rivastigmine patch administration + 1).

The duration of exposure (in days) will be summarized for the safety set as

- a continuous variable with the standard descriptive statistics, and
- a categorical variable classified into <=4 weeks, >4 to <=8 weeks, >8 to <=12 weeks, >12 to <=16 weeks, >16 to <=20 weeks and >20 to <=24 weeks.

A data listing of the drug doses administered by patients will be provided.

The number and percentage of patients who could stay on 1-step titration and switched 3 step titration will also be provided separately.

Investigator reported compliance from eCRF

Compliance will be calculated based on the DAR data. Compliance data will be summarized descriptively as a continuous and categorical variable.

The number and percentages of patients in each of the compliance categories mentioned in the eCRF, i.e., Poor (< 25%), Average ($\geq 25\%$ to < 50%), Good ($\geq 50\%$ to < 75%), Very good ($\geq 75\%$ to $\leq 100\%$) and Overdose or misuse (>100%) will be summarized. In case of over compliance (> 100%) the reason will be listed.

Additional summaries will be presented for each compliance category stated above for the following subgroups,

- use of skin moisturizer at baseline (yes/no)
- use of skin management at least one time during study period (yes/no)
- inadequate compliance with the ChE inhibitors at screening and baseline (yes/no)
- inadequate treatment (efficacious dose was not reached or inadequate compliance) with the ChE inhibitors because of AEs except gastrointestinal (GI) symptoms (nausea and vomiting) at screening and baseline (yes/no)
- swallowing difficulties at screening and baseline (yes/no)

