2.6.2 Safety analyses

All safety variables will be reported using the safety set.

In addition, the adverse events, serious adverse events and adverse events of special interest summaries described in the following sub-sections will also be presented by the safety subgroups specified in [Section 2.2.1.2](#).

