2.6.2.1 Adverse events (AEs)

All adverse events starting on or after the first treatment will be included in all summaries and will also be listed. Adverse events occurring after signing of the informed consent prior to the start of study treatment will be listed only.

These adverse events will also be summarized by overall, by study periods as Week 1 to Week 4, Week 4 to Week 8, Week 8 to Week 12, Week 12 to Week 16, Week 16 to Week 20 and Week 20 to Week 24 by the following variables.

Adverse events by SOC and PT

All adverse events starting on or after the first treatment will be coded utilizing the MedDRA dictionary, tabulated, and analyzed by primary system organ class and preferred term.

Primary system organ classes will be sorted alphabetically and, within each primary system organ class, the preferred terms will be sorted in descending order of frequency.

If a patient reported more than one adverse event with the same preferred term, the adverse event will be counted only once. If a patient reported more than one adverse event within the

same primary system organ class, the patient will be counted only once at the system organ class level.

AEs by severity

All adverse events will be summarized by maximum severity, primary system organ class and preferred term. If a patient reports more than one adverse event within the same primary system organ class, only one adverse event will be counted for that patient at the highest severity level in the total row for each primary system organ class. If a patient reported more than one adverse event with the same preferred term, the highest (maximum) severity will be presented. Missing severity will be assumed to be severe in the summary table.

AEs suspected to be related to study drug

The treatment emergent adverse events suspected to be related to study drug (according to the investigators) will be summarized by primary system organ class and preferred term. Relationship to study drug is considered as suspected for those events where "Relationship to study drug" is answered by the investigator as "Suspected".

AEs leading to permanent study drug discontinuation

Treatment emergent adverse events leading to permanent study drug discontinuation, regardless of study drug relationship, will be summarized by primary system organ class and preferred term.

AEs requiring dose adjustment or interruption

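### Adverse-event tables split by titration regimen and by skin management at any time can count an event in the group it helped create; whole-safety-set tables are unaffected

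*SAP*

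**What the plan says.** Protocol 5.2 states that "all of the patients will be assigned to 1-step titration treatment", and Protocol 5.5.4 that "all patients will start study treatment with one rivastigmine patch of 9 mg once a day". The move to 3-step is described in Protocol 5.1.1: "If patients cannot tolerate 1-step titration method to reach the maintenance patch dose of 18 mg/day", the investigator may switch the patient. SAP 2.1.1.1 says the same. SAP 2.2.1.2 lists AEs as one recorded reason for switching, among others.

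SAP 2.2.1.2 applies its safety subgroups to all AE summaries of SAP 2.6.2.1. One is "treatment regimen (overall, 1-step and 3-step titration"). Another, profile 1b, is skin management used at least once in the study period, identified from the medication page and confirmed by the clinical team. Application-site reactions are explicitly tabulated by 1b. Protocol 5.5.4 allows topical steroids or antihistamines to be started when a skin reaction appears.

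SAP 2.6.2.1 states: "All adverse events starting on or after the first treatment will be included in all summaries and will also be listed". No text says which regimen column an AE enters, or requires skin management to precede the event. Elsewhere the SAP treats regimen as a property of the patient: "The per protocol set will include all patients in the FAS who had only 1 step titration" (SAP 2.2) and "The number and percentage of patients who could stay on 1-step titration and switched 3 step titration will also be provided separately" (SAP 2.4.1). SAP 2.5.4 analyses 1-step and 3-step patients as separate sets.

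The main AE tables are not split. SAP 2.6.2 says "All safety variables will be reported using the safety set" and presents the subgroup tables in addition.

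**The concern.** Both groupings form after treatment starts, and an AE can be what forms them. A patient who has an AE on 1-step and switches because of it is, under a per-patient label, a 3-step patient in every table. The AE leaves the 1-step column and enters 3-step, although 1-step was in force when it arose. A patient whose skin reaction is treated becomes a 1b user, and the reaction is then counted among users.

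A reader who sets 1-step beside 3-step, or users beside non-users, would see differences made by the grouping rule. In any-AE tables the distortion favours 1-step, the regimen this study is about. In application-site tables it counts against skin care.

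The same list splits AEs by treatment retention and by overall compliance, both also fixed after baseline. Retention (defined in SAP 2.11.1) requires completing the study on 18 mg, so AEs leading to discontinuation fall almost wholly in the no group by definition.

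**Working it through.** The plan states no switch rate, skin-care rate or expected difference on this point, so there is no planned figure to reproduce. From the documents come 120 planned patients (SAP 3) and 15.0% (16/107) stopping for an AE on 1-step in the earlier titration study (Protocol 3.6). All other rates are assumptions, and no effect of regimen or skin care is assumed throughout.

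**Regimen, any AE.** Let s be the share who switch, a the share of switches that follow an AE, and p the any-AE risk in all other patients.
- 3-step column = a + (1 − a)p; 1-step column = p.
- Overall = s[a + (1 − a)p] + (1 − s)p.
- Overall minus 1-step = s·a·(1 − p).
- Low case, s = 0.10, a = 0.5, p = 0.7: 0.10 × 0.5 × 0.3 = 0.015, or 1.5 points; 3-step shows 85%.
- High case, s = 0.20, a = 1, p = 0.5: 0.20 × 1 × 0.5 = 0.10, or 10 points; 3-step shows 100%.
- With a = 0.5 and p = 0.5, 3-step shows 75%.
- Patients whose triggering AE changes column = 120·s·a: 120 × 0.10 × 0.5 = 6, to 120 × 0.20 × 1 = 24.

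**Regimen, over time.** A simulation in 24 weekly steps with 150,000 patients was calibrated to 60% with any AE and 15% stopping for an AE. It assumes a 0.15 probability of switching after an AE and no other switching. Five hazard models were used: constant; gamma frailty with shape 1 or 0.5; falling 7% or 15% a week.

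| Model | 1-step shortfall, switching in Weeks 1–24 | Shortfall, switching in Weeks 1–8 only | AEs per 100 patient-weeks by regimen in force, 1-step v 3-step (switching in Weeks 1–24) |
|---|---|---|---|
| Constant | 4.4 | 1.5 | 3.8 v 3.8 |
| Frailty, shape 1 | 6.5 | 2.4 | 5.1 v 9.7 |
| Frailty, shape 0.5 | 9.6 | 3.9 | 7.1 v 19.5 |
| Falling 7% | 4.3 | 2.3 | 3.9 v 3.0 |
| Falling 15% | 4.3 | 3.1 | 4.0 v 2.4 |

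Shortfalls are in percentage points. About 10–19% switch when switching is open throughout, and 4–9% when it is confined to Weeks 1–8, the titration phase in which Protocol 3.1 describes the option. Protocol 5.5.5 leaves some later switching possible. The last column shows that counting by regimen in force does not equalise the columns either.

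**Skin events by 1b.** Let v be preventive use, r the reaction risk and t the share of reactors treated.
- Users = [vr + (1 − v)rt] / [v + (1 − v)rt]; non-users = r(1 − t) / (1 − rt).
- v = 0.7, r = 0.2, t = 0.2: 0.152/0.712 = 21.3% v 0.16/0.96 = 16.7%, a gap of 4.7 points.
- v = 0.2, r = 0.4, t = 0.7: 0.304/0.424 = 71.7% v 0.12/0.72 = 16.7%, a gap of 55 points.
- v = 0.1, r = 0.6, t = 0.9: 0.546/0.586 = 93.2% v 0.06/0.46 = 13.0%, a gap of 80 points.

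In every case the two groups recombine to the same overall percentage, so unsplit tables do not move.

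**The case against.** The strongest reply is that little depends on these tables. The safety of 1-step is read from the whole safety set, no between-regimen safety test is planned, and SAP 2.1.1.1 openly describes switchers as patients who could not tolerate 1-step. This stands, and it is why the point is minor.

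Other tables partly show what happened: AEs by 4-week period, by reason for switching, and AEs requiring dose adjustment or interruption. Moisturizer use at baseline (profile 1a) is a split that no later AE can create. This also stands, but none of it changes what the regimen and 1b columns contain.

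The per-patient label is an inference. That is correct. It is the reading that fits SAP 2.2, 2.4.1 and 2.5.4, and if another was meant the SAP needs to say so. Likewise, skin management is not defined; preventive use dilutes the effect, and whether reactive topical treatment counts is left to the clinical team.

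Counting by regimen in force does not make the columns comparable, as the table shows. It corrects where an AE is attributed, so a footnote is needed as well.

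**Conclusion.** The point holds as a minor defect in supplementary descriptive tables. On the per-patient reading, an AE that leads to a switch is tabulated under 3-step, and a treated skin reaction is tabulated under skin-management users. If AEs influence switching and skin treatment, the 1-step any-AE percentage falls below overall, 3-step is inflated, and users look worse on application-site events with no real effect. The size cannot be derived from the documents. About 1.5 to 10 points for the 1-step shortfall, and about 5 to 80 points for the skin gap, are illustrations under assumed rates and not bounds.

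A reader might infer three stronger things that the documents do not support.
- That the trial's safety conclusion on 1-step is biased. It is not: the safety set all started 1-step and is reported whole.
- That 1-step is also flattered on AEs leading to discontinuation. The direction is open: with switching in all 24 weeks, the simulation gives 15.8% v 7.9% (1-step v 3-step) under a constant hazard and 14.1% v 18.9% under frailty of shape 0.5. No direction is claimed for gastrointestinal events or for retention by 1b either.
- That rates by regimen in force would give a valid comparison. Switchers are selected for AEs, and their 3-step time always comes later.

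**What to change.** 1. In the regimen AE tables, assign each AE to the regimen in force at onset, with onset on the switch date counted as 1-step, and show the exposure time under each regimen, stating how days without a patch before the switch are counted. Footnote that the groups form after baseline, that switchers are selected for AEs and that 3-step time is always later. The columns are therefore descriptive and not a comparison of regimens, and the safety of 1-step is read from the whole safety set.
2. Define skin management before database lock. For application-site AEs by 1b, separate events with onset before the start of skin management from those after it, and point the reader to 1a as the split a later AE cannot create.
3. Footnote the AE splits by retention and by overall compliance, and retention by 1b, as defined after baseline and not interpretable as effects.

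The cost is SAP wording, footnotes and some programming, using dates already collected on the dosing, AE and medication pages. No study procedure changes. The 3-step groups will be small: at an assumed 10–20% switching, 12 to 24 of 120 patients. The 95% half-width, 1.96·√[p(1 − p)/n], is about 25 points at n = 12, p = 0.75, and about 14 points at n = 24, p = 0.85.

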2.3 Patient disposition, demographics and other baseline characteristics

Patient demographic and baseline characteristics will be captured at Visit 1 or Visit 2 (only if the variable is not already captured at Visit 1). All the baseline and demographic characteristics will be summarized using the FAS in the CSR.

2.3.1 Patient disposition

The FAS will be used for the summary and listing of patient disposition.

The number and percentage of patients screened, completed and discontinued the study (and/or treatment) will be summarized for FAS population.

The overall number of patients who were screened, completed the study and discontinued from the study (and/or treatment) will also be summarized with reasons for premature discontinuation.

Patient identification number and whether they completed or discontinued from the study (and/or treatment) will be listed, with date of last dose and primary reason for premature discontinuation.

2.3.2 Medical history/current medical condition

Medical history will be coded using the Medical Dictionary for Regulatory Activities terminology (MedDRA, current version at database lock). History/conditions will be summarized for the safety set by primary system organ class and preferred term, and overall. Verbatim recorded history/conditions will be listed together with the coded terms, date of diagnosis/surgery and whether the problem was ongoing at start of the study.

2.4 Treatments (study treatment, rescue medication, concomitant therapies, compliance)

2.4.1 Study treatment exposure / compliance

Duration of exposure to the study treatment (rivastigmine patch) will be calculated as the number of days exposed to the treatment with rivastigmine patch over the specified period (expressed as: Duration of exposure = last known date of rivastigmine patch administration – first known date of rivastigmine patch administration + 1).

The duration of exposure (in days) will be summarized for the safety set as

- a continuous variable with the standard descriptive statistics, and
- a categorical variable classified into <=4 weeks, >4 to <=8 weeks, >8 to <=12 weeks, >12 to <=16 weeks, >16 to <=20 weeks and >20 to <=24 weeks.

A data listing of the drug doses administered by patients will be provided.

The number and percentage of patients who could stay on 1-step titration and switched 3 step titration will also be provided separately.

Investigator reported compliance from eCRF

Compliance will be calculated based on the DAR data. Compliance data will be summarized descriptively as a continuous and categorical variable.

The number and percentages of patients in each of the compliance categories mentioned in the eCRF, i.e., Poor (< 25%), Average ($\geq 25\%$ to < 50%), Good ($\geq 50\%$ to < 75%), Very good ($\geq 75\%$ to $\leq 100\%$) and Overdose or misuse (>100%) will be summarized. In case of over compliance (> 100%) the reason will be listed.

Additional summaries will be presented for each compliance category stated above for the following subgroups,

- use of skin moisturizer at baseline (yes/no)
- use of skin management at least one time during study period (yes/no)
- inadequate compliance with the ChE inhibitors at screening and baseline (yes/no)
- inadequate treatment (efficacious dose was not reached or inadequate compliance) with the ChE inhibitors because of AEs except gastrointestinal (GI) symptoms (nausea and vomiting) at screening and baseline (yes/no)
- swallowing difficulties at screening and baseline (yes/no)

2.4.2 Prior, concomitant and post therapies

Each medication has the start and end dates recorded. Prior medications are defined as those medications which were taken and stopped prior to the first dose of study drug. Concomitant medications are defined as those medications which were taken on or after the first dose of study drug but not prior to the first dose of study drug. Prior/concomitant medications are defined as those medications which were taken prior to and continued after the first dose of the study drug. All prior and concomitant medications will be summarized by primary system organ class and preferred term. All prior/concomitant medications will be summarized as concomitant medications, and will not be included in prior medication outputs. All concomitant medications are also summarized by primary system organ class and preferred terms.

Surgical and medical procedures (non-drug therapies) will be summarized by primary system organ class and preferred term. All summaries will be on the safety set.

2.5 Analysis of the primary objective

The primary objective is to evaluate the efficacy of rivastigmine patch with 1-step titration on cognitive function for mild to moderate AD patients who failed to benefit from other ChEIs as change from baseline to Week 24 in the total score of Mini-Mental State Examination (MMSE).

